14.2 Analysis of Secondary Endpoints

1. Efficacy Endpoints

- a.** EASI and IGA scores at week 16 will be compared to baseline.

2. Safety Endpoints

- a.** Safety will be evaluated by tabulation of adverse events (AEs), including any Serious Adverse Events (SAEs) within treatment groups. All AEs occurring during the study will be recorded. Descriptions of adverse events will include the date of onset, the date the adverse event ended, the severity of the adverse event, and the outcome. All reported adverse events will be summarized by the number of subjects reporting adverse events, body system, severity, seriousness, and relationship to study treatment.

3. Analysis of Other Endpoints

- a.** Other variables may be analyzed and presented descriptively. The methods to be used will include (but are not limited to) parametric and nonparametric analysis, means, standard deviations, frequency counts and graphs, as appropriate.
- b.** Video footage of patient experiences will be compiled at the end of the study. The compiled video footage will subsequently be watched and analyzed to further understand the experiences of atopic dermatitis patients, and how undergoing dupilumab treatment alters these patients' experiences and attitudes with their skin disease.

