1 BACKGROUND

Atopic dermatitis (AD) is a common, complex, immune-mediated condition affecting 5-15% of children and adults worldwide. Adults with AD suffer from severe pruritus and inflammatory skin rash with a chronic disease course.

Patients with moderate-to-severe AD report a multidimensional burden including itch, pain, sleep disturbance, anxiety and depression, and impaired health-related quality-of-life (HRQoL). Patients suffering from AD are more likely to be depressed when compared to the general population, which can lead to increased suicidal ideation. Furthermore, AD can create a negative impact in the workplace, as patients with the disease are more likely to miss work due to their skin symptoms. With the significant negative psychosocial impact of AD, patients not only want to improve their skin lesions, but also their personal experience with this chronic disease.

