9.1.11 Video recording

Patients will be given a video recording device at week 0, and will be instructed on how to use it to record video. Patients will be instructed to record videos of themselves at home discussing their experience with the study drug and its impact on their skin and quality of life for roughly 5-10 minutes/week. The patient will be the only person in the video (i.e. there will be no family members or others interviewing or participating in the video). The patient will be encouraged to

record in a private setting (i.e. alone in their bedroom or office) and similarly, will be instructed to keep the recording device and its stored footage in a private location. Patients will be given a list of topics at the week 0 visit to be used as guidelines for discussion:

- 1) Please discuss any changes you have observed in your skin while using the study drug.
- 2) What is the most important change that you have experienced while using the study drug?
- 3) What are your goals with undergoing this medication for the future?
- 4) Please discuss how these changes in your skin have impacted both your life (day-to-day behaviors such as clothing choice or activities) and the lives of your loved ones.
- 5) Please discuss any changes in how you feel since starting the study medication (mood, sleep, work, home life, personal relationships).
- 6) Please discuss your overall experience using the study drug.
- 7) Please discuss any interesting or notable experiences or events that have occurred to you while using the study drug.
- 8) Please feel free to discuss anything else pertaining to your experience with eczema

Patients will be instructed to bring in their video recording devices to their study visits at weeks 4, 8, 12, 16, 20, 24, 28, 32, 36, 40, 44, 48, 52, and at early termination when applicable. At these visits, study staff will download the patient videos to a secure local storage site.

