11 ADVERSE EXPERIENCE REPORTING AND DOCUMENTATION

11.1 Adverse Events

Definition of an AE: Any untoward medical occurrence in a subject administered a pharmaceutical product that does not necessarily have a causal relationship with the treatment. An AE can therefore be any unfavorable and unintended sign (including an abnormal laboratory finding), symptom, or disease temporally associated with the use of a medicinal (investigational) product, whether or not considered related to the investigational medicinal product.

Investigational Medicinal Product (IMP) includes the drug under evaluation and the comparator drug(s) if specified as part of the research objective, given at any time during the study. Medical conditions/diseases present before starting the drug of interest are only considered adverse events if they worsen after starting the drug of interest.

The occurrence of adverse events will be sought by non-directive questioning of the patient at each visit during the study. Adverse events also may be detected when they are volunteered by the patient during or between visits or through physical examination, laboratory test, or other assessments. All adverse events will be recorded in the study database including the following information:

1. the severity grade (mild, moderate, severe)
2. its relationship to the drug(s) of interest (suspected/not suspected)
3. its duration (start and end dates or if continuing at final exam)
4. whether it constitutes a serious adverse event (SAE)

AE Severity

The National Cancer Institute's Common Terminology Criteria for Adverse Events (CTCAE) Version 3.0 should be used to assess and grade AE severity, including laboratory abnormalities judged to be clinically significant. The modified criteria can be found in the study manual. If the experience is not covered in the modified criteria, the guidelines shown in **Error! Reference source not found.** below should be used to grade severity. It should be pointed out that the term "severe" is a measure of intensity and that a severe AE is not necessarily serious.

Table 1. AE Severity Grading

Severity (Toxicity Grade)	Description
Mild (1)	Transient or mild discomfort; no limitation in activity; no medical intervention or therapy required. The subject may be aware of the sign or symptom but tolerates it reasonably well.
Moderate (2)	Mild to moderate limitation in activity, no or minimal medical intervention/therapy required.

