11.3. Serious Adverse Experience Reporting

Study sites will document all SAEs that occur (whether or not related to study drug) per [UCSF CHR Guidelines](#). The collection period for all SAEs will begin after informed consent is obtained and end after procedures for the final study visit have been completed.

SAEs occurring after four weeks from ending study participation should only be reported if considered by the Investigator attributable to the exposure to the investigational drug(s) during the trial period. This includes the period in which the study protocol interferes with the standard medical treatment given to a subject, even if study treatment has not yet started (e.g. withdrawal of previous treatment during washout period, change in treatment to a fixed dose of concomitant medication).

In accordance with the standard operating procedures and policies of the local Institutional Review Board (IRB)/Independent Ethics Committee (IEC), the site investigator will report SAEs to the IRB/IEC.

Timelines: All serious adverse events (SAEs) must be reported by the sites to Sponsor within 24 hours of occurrence of the SAE. The timelines for investigator initiated trials reporting to Regeneron Pharmaceuticals will be done as per Third Party Study/Investigator Initiated Trial Agreement. All reports must be sent to Regeneron as below:

- Fax SAE/CIOMS or MedWatch Reports to [contact]
- Email forms to [contact]

Follow-up reports: SAEs will be followed until resolution or until it is judged to be permanent, and an assessment will be made at each visit (or more frequently, if necessary) of any changes in severity, the suspected relationship to the drug of interest, the interventions required to treat it, and the outcome.

The Sponsor shall support Regeneron in the following-up of all SAEs so that complete information is available to maintain patient safety and also as part of any commitments by Regeneron to any Health authority OR specific Health authority follow-up requests for the product under investigation.

Pregnancies: Any occurrences of a pregnancy in a patient (or a patients partner) during study participation will be collected. All pregnancies will be followed up to determine outcome, including spontaneous or voluntary termination, details of the birth, and the presence or absence of any birth defects, congenital abnormalities, or maternal and/or newborn complications.

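### An adverse event disclosed only in a subject's weekly video has no route into AE or SAE handling and would be heard only after the study ends

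*Combined protocol and SAP*

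**What the plan says.** **What is recorded.** Section 9.1.11 gives each subject a recording device at Week 0. Subjects record alone at home, "discussing their experience with the study drug and its impact on their skin and quality of life for roughly 5-10 minutes/week". The suggested topics include "Please discuss any changes in how you feel since starting the study medication (mood, sleep, work, home life, personal relationships" and "Please discuss any interesting or notable experiences or events that have occurred to you while using the study drug".

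**What the site does with it.** Subjects bring the device in on this schedule: "weeks 4, 8, 12, 16, 20, 24, 28, 32, 36, 40, 44, 48, 52, and at early termination when applicable. At these visits, study staff". The rest of that sentence has the files copied to secure local storage. Visit lists 10.03 to 10.16 carry the same single video task, which is to download. None includes viewing.

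**When it is watched.** Section 14.2: "Video footage of patient experiences will be compiled at the end of the study. The compiled video footage will subsequently be watched and analyzed". The stated purpose is to understand patients' experiences and attitudes. Safety is not mentioned.

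**What the safety sections require.** Section 11.1: "All adverse events will be recorded in the study database including the following information". AEs are sought by non-directive questioning at each visit, and may also be volunteered by the patient or come to light through other assessments. Videos are not named. Section 11.3: "All serious adverse events (SAEs) must be reported by the sites to Sponsor within 24 hours of occurrence of the SAE". It also asks for SAEs to be reassessed at each visit until they resolve or are judged permanent.

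**The concern.** The videos are a channel that the study itself opens, and two of its prompts ask about matters that can include adverse events. The site holds the files within weeks, yet the plan does not have anyone open them until the study is over, and it does not say what happens to an event heard then.

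The background section gives a reason to care about the mood prompt in particular. It links the disease to depression, "which can lead to increased suicidal ideation".

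Two things are at stake for an event told only on video:

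- **Follow-up of the subject.** The last injection is at Week 50 and the last visit at Week 52. Viewing after the study leaves no scheduled visit at which the event could be assessed or followed.
- **Quality of the safety endpoint.** Safety is a secondary endpoint, and section 14.2 wants onset date, end date, severity and outcome for each AE. These are hard to reconstruct a year or more later.

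**Working it through.** **Inputs**

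- Duration: 52 weeks of recruitment and 52 weeks of visits, stated total 104 weeks (synopsis).
- Subjects: up to 30 (section 14.3).
- Recording: about 5 to 10 minutes a week (section 9.1.11).
- Downloads: Weeks 4 to 52, every 4 weeks (section 9.1.11).

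**1. The plan's own figure.** 52 + 52 = 104 weeks, as stated.

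**2. Number of downloads.** (52 − 4)/4 + 1 = 13 per subject, so 30 × 13 = 390 at most on the visit schedule.

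**3. Wait from download to earliest viewing.** Assume that viewing starts as soon as the last subject finishes. If the last subject enrols R weeks after the first, the first subject's Week 4 file waits R + 52 − 4 = R + 48 weeks.

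- First subject, R = 52: 104 − 4 = 100 weeks.
- Last subject: 52 − 4 = 48 weeks, whatever R is.

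If end of study is read as each subject's own end, the wait is 48 weeks for everyone.

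**4. Wait from recording to earliest viewing, with R = 52.**

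| Subject | Shortest (Week 52 video) | Longest (Week 1 video) | Mean over 52 weekly videos |
|---|---|---|---|
| Last enrolled | 52 − 52 = 0 | 52 − 1 = 51 | 25.5 weeks |
| First enrolled | 104 − 52 = 52 | 104 − 1 = 103 | 77.5 weeks |

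**5. Comparison: viewing at each download.** A video is recorded at most 3 weeks before the next download week, so the wait is 0 to 3 weeks, mean (0 + 1 + 2 + 3)/4 = 1.5 weeks.

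**6. Amount of footage.**

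- Per download: 4 × 5 = 20 to 4 × 10 = 40 minutes.
- Whole study: 30 × 52 × 5/60 = 130 to 30 × 52 × 10/60 = 260 hours.

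**7. What cannot be computed.** The documents give no rate at which an event would be told on video and nowhere else. The number of AEs affected is therefore unknown.

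**The case against.** The strongest reply is that the videos are an extra channel on top of a working AE system. AE review and an interim medical history take place at every visit where files are downloaded. Patients may volunteer events between visits, and section 10.01 gives them a number to call about symptoms. PGWB, PSQI, WPAI, DLQI and the itch and pain scales are completed at every visit from Week 0, so mood, sleep and work are measured every 4 weeks. All of this stands, and it limits the concern to events told on video and nowhere else. It does not close the gap, because none of these routes looks at what was said on video and the visit questioning is non-directive.

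A reader might infer more than the documents support:

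- **That adverse events in general are missed.** The parallel routes above rule out so broad a reading.
- **That late-found events are left out of the AE tables.** Section 14.2 does not say whether viewing comes before or after database lock, and section 15.1 has the investigator review all data, with no time set. The plan is silent; it does not exclude them.
- **That earlier viewing would rescue the 24-hour SAE requirement.** That clock runs from occurrence. A lag of 0 to 3 weeks would usually miss it too. Deaths and hospitalizations are also unlikely to be known only from a video.
- **That subjects are never told the videos go unmonitored.** The protocol text does not tell them, but the consent pages are not available for review and may do so.
- **That the prompts ask about suicidality.** They do not. The topics are discussion guidelines, and the background describes an association with the disease.

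There is also a fair point on cost. Section 14.2 says that compiled footage will be watched, which may be less than every raw minute. Safety viewing of all 390 downloads could thus add up to 130 to 260 hours, partly duplicated by the final analysis.

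**Conclusion.** The point holds for adverse events disclosed only on video. The study solicits such statements weekly and collects them every 4 weeks, but the plan schedules viewing after the study and gives the content no route to AE or SAE handling. An event told in the first month would be heard about 48 to 100 weeks after the Week 4 download, and after that subject's last injection and last visit.

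The 100-week end assumes that recruitment takes the full 52 weeks and concerns the first subject enrolled. Both ends assume that viewing starts at once when the study ends, so they are minimum waits.

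This is a gap in the plan; no two passages contradict each other. The number of events affected is unknown and may be small. The case for acting rests on the low cost of closing the gap. It does not depend on showing that AE capture as a whole fails.

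**What to change.** 1. **Section 9.1.11:** at device sign-out, instruct subjects that the videos are not monitored in real time and that health or mood problems must be reported through the contact number given at consent (section 10.01). If the consent form already says this, align the two texts.
2. **Sections 10.03 to 10.16:** add one question to the AE review, asking whether the subject described any health or mood problem on video since the last visit.
3. **Section 11.1:** allow this one directed question alongside the non-directive questioning, so that the two do not conflict.
4. **Section 14.2:** state that any event found at end-of-study viewing is entered as an AE or SAE before database lock and tabulation.

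Having existing staff view each download at the visit is optional. It would shorten the wait from recording to viewing to 0 to 3 weeks, but could take up to 130 to 260 hours, some of it spent on footage watched again at the end.

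**Cost of items 1 to 4:** protocol wording, one instruction per subject, and about a minute per visit (an assumption), so 390 × 1/60 = 6.5 hours over the whole study. The directed question will probably raise the number of solicited AEs slightly, which the safety summary should mention.

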14.3 Sample Size

Up to 30 subjects will receive dupilumab for a treatment period of 52 weeks (i.e. last injection on week 50). This is based on previous similar studies investigating the impact of adalimumab and ustekinumab on QoL in psoriasis patients which included 33 and 36 patients, respectively.

15 DATA COLLECTION, RETENTION AND MONITORING

15.1 Data Collection Instruments

The Investigator will prepare and maintain adequate and accurate source documents designed to record all observations and other pertinent data for each subject. Study personnel at each site will enter data from source documents corresponding to a subject's visit into the protocol-specific electronic (eCRF) or paper Case Report Form when the information corresponding to that visit is available. Patient recorded videos will be downloaded to a secure storage site. Subjects will not be identified by name in the study database or on any study documents, but will be identified by a site number, subject number and initials.

If a correction is required for an eCRF, the time and date stamps track the person entering or updating eCRF data and creates an electronic audit trail. If a correction is made on a paper CRF, the study staff member will line through the incorrect data, write in the correct data and initial and date the change.

The Investigator is responsible for all information collected on subjects enrolled in this study. All data collected during the course of this study must be reviewed and verified for completeness and accuracy by the Investigator. A copy of the CRF will remain at the Investigator's site at the completion of the study.

15.2 Data Management Procedures

The data will be entered into a validated database. The Data Management group will be responsible for data processing, in accordance with procedural documentation. Database lock will occur once quality assurance procedures have been completed.

All procedures for the handling and analysis of data will be conducted using good computing practices meeting FDA guidelines for the handling and analysis of data for clinical trials.

15.3 Data Quality Control and Reporting

After data have been entered into the study database, a system of computerized data validation checks will be implemented and applied to the database on a regular basis. On eCRFs, queries are entered, tracked, and resolved through the EDC system directly. On paper, query reports (Data Clarification Requests) pertaining to data omissions and discrepancies will be forwarded to the Investigators and study monitors for resolution. The study database will be updated in accordance with the resolved queries. All changes to the study database will be documented.

15.4 Archival of Data

The database is safeguarded against unauthorized access by established security procedures;

appropriate backup copies of the database and related software files will be maintained. Databases are backed up by the database administrator in conjunction with any updates or changes to the database.

At critical junctures of the protocol (e.g., production of interim reports and final reports), data for analysis is locked and cleaned per established procedures.

15.5 Availability and Retention of Investigational Records

The Investigator must make study data accessible to the monitor, other authorized representatives of the Sponsor (or designee), IRB/IEC, and Regulatory Agency (e.g., FDA) inspectors upon request. A file for each subject must be maintained that includes the signed Informed Consent, HIPAA Authorization and Assent Form and copies of all source documentation related to that subject. The Investigator must ensure the reliability and availability of source documents from which the information on the CRF was derived.

All study documents (patient files, signed informed consent forms, copies of CRFs, Study File Notebook, etc.) must be kept secured for a period of two years following marketing of the investigational product or for two years after centers have been notified that the IND has been discontinued. There may be other circumstances for which the Sponsor is required to maintain study records and, therefore, the Sponsor should be contacted prior to removing study records for any reason.

15.6 Subject Confidentiality

In order to maintain subject confidentiality, only a site number, subject number and subject initials will identify all study subjects on CRFs and other documentation submitted to the Sponsor. Additional subject confidentiality issues (if applicable) are covered in the Clinical Study Agreement.

16 ADMINISTRATIVE, ETHICAL, REGULATORY CONSIDERATIONS

The study will be conducted according to the Declaration of Helsinki, Protection of Human Volunteers (21 CFR 50), Institutional Review Boards (21 CFR 56), and Obligations of Clinical Investigators (21 CFR 312).

To maintain confidentiality, all laboratory specimens, evaluation forms, reports and other records will be identified by a coded number and initials only. All study records will be kept in a locked file cabinet and code sheets linking a patient's name to a patient identification number will be stored separately in another locked file cabinet. Clinical information will not be released without written permission of the subject, except as necessary for monitoring by the FDA. The Investigator must also comply with all applicable privacy regulations (e.g., Health Insurance Portability and Accountability Act of 1996, EU Data Protection Directive 95/46/EC).

16.1 Protocol Amendments

Any amendment to the protocol will be written by the PI or a sub-investigator with the PI's

approval. Protocol amendments cannot be implemented without prior written IRB/IEC approval except as necessary to eliminate immediate safety hazards to patients. A protocol amendment intended to eliminate an apparent immediate hazard to patients may be implemented immediately, provided the IRBs are notified within five working days.

16.2 Institutional Review Boards and Independent Ethics Committees

The protocol and consent form will be reviewed and approved by the IRB/IEC of each participating center prior to study initiation. Serious adverse experiences regardless of causality will be reported to the IRB/IEC in accordance with the standard operating procedures and policies of the IRB/IEC, and the Investigator will keep the IRB/IEC informed as to the progress of the study. The Investigator will obtain assurance of IRB/IEC compliance with regulations.

Any documents that the IRB/IEC may need to fulfill its responsibilities (such as protocol, protocol amendments, Investigator's Brochure, consent forms, information concerning patient recruitment, payment or compensation procedures, or other pertinent information) will be submitted to the IRB/IEC. The IRB/IECs written unconditional approval of the study protocol and the informed consent form will be in the possession of the Investigator before the study is initiated. The IRB/IECs unconditional approval statement will be transmitted by the Investigator to the designee prior to the shipment of study supplies to the site. This approval must refer to the study by exact protocol title and number and should identify the documents reviewed and the date of review.

Protocol and/or informed consent modifications or changes may not be initiated without prior written IRB/IEC approval except when necessary to eliminate immediate hazards to the patients or when the change(s) involves only logistical or administrative aspects of the study. Such modifications will be submitted to the IRB/IEC and written verification that the modification was submitted and subsequently approved should be obtained.

The IRB/IEC must be informed of revisions to other documents originally submitted for review; serious and/or unexpected adverse experiences occurring during the study in accordance with the standard operating procedures and policies of the IRB; new information that may affect adversely the safety of the patients of the conduct of the study; an annual update and/or request for re-approval; and when the study has been completed.

